For imaging outcomes, topography and subjective effects, all relevant outcome variables will first be examined with descriptive statistical analyses that focus on describing and understanding patterns and distributions. We will identify any potential outliers, assess distributional assumptions, and apply appropriate transformations if the normality assumption is violated. To test the impact of pH of e-liquid vaped on rate and concentration of [¹¹C]-nicotine uptake in the brain and lung regions, and subjective effects, the primary comparison arms will be free-base vs. nicotine salt-based nicotine e-liquid. For each hypothesis we will compare the difference in mean outcomes (post – pre-vaping bout, where appropriate) per laboratory session using the mixed effects modeling approach for repeated measures analysis of variance that uses a random effects model to account for multiple observations from the same study subject's outcome measures.

Conceptually, the analysis approach reduces to a simple paired t-test for parametric analysis or Wilcoxon signed-rank test for non-parametric analysis... This approach allows for proper treatment of the multiple observations per study subject's outcome data by accounting for the correlation of data observations within the same study subject's outcome. Mixed effects modeling also allows for the dataset to have some missing values, unequal time points between subjects, and flexible covariance structures.. Pairwise comparisons will be adjusted for multiple testing procedures. All statistical tests will be two-tailed, and no assumptions are made *a priori* about the direction of potential differences in primary outcome distributions.

J. Gender/Minority/Pediatric Inclusion for Research

i. Inclusion of Women and Minorities

According to U.S. Census Data, 53% of Winston-Salem residents are female. In our previous studies with smokers, 55-62% of participants were female. In Winston-Salem, racial composition is 56% White, 35% Black or African American, 2% Asian, 0.2% American Indian/Alaska Native, 0.1% Native Hawaiian/Other Pacific Islander, and 3% two or more races. The ethnic composition of individuals living in Winston-Salem is 6% and 15% Hispanic/Latino, respectively. We expect that our distributions will be similar to these but we may potentially have a larger distribution of ethnic and racial minorities, based on our team's previous studies. However, we will continuously monitor enrollment in order to ensure that we are meeting recruitment goals to avoid under-recruiting minorities. If the targeted enrollment for minorities is not met because they do not respond to the advertisements, we will make special efforts to solicit their participation by advertising in community newspapers and community centers.

ii. Inclusion of Children

Participation in the proposed study will be restricted to individuals 21 years of age and older. This exclusion is because the use of tobacco products by minors is illegal and the concern of introducing and potentially addicting children and adolescents to another tobacco product (i.e., electronic cigarettes).

K. Human Participants

i. Potential Risks

The research protocol calls for current e-cigarette users to use a study e-cigarette. The participants are already using e-cigarettes and will only be asked to use what will be a fully characterized e-cigarette device and e-liquids for which an FDA ITP will be submitted and "approved" (i.e., receive an FDA letter of "no concern"). Questionnaires, saliva, and exhaled breath procedures are all non-invasive and involve minimal risk to study participants. Potential risks are as follows: a) risk of using e-cigarettes, b) risk associated with radioactivity exposure, c) loss of confidentiality or privacy, and d) lack of appropriate storage of nicotine-containing products in a house with children and pets.

ii. Protections Against Risk

a) Recruitment and Informed Consent:

At first contact, all participants will be screened according to the study's inclusion/exclusion criteria. Those who are eligible will be given a brief verbal overview of the study and invited to participate. Informed consent (including a description of the nature, purpose, risks, and benefits of the study) will take place through oral explanation of the study. The voluntary nature of the study and the participant's right to withdraw at any time will be stressed during the consent process. A copy of the informed consent will be provided to the participant in written form at the time of consent for them to keep. Informed consent will be collected by IRB-approved study personnel. The Ohio State University Institutional Review Board will approve recruitment script and materials, consent forms, and all study procedures. All participants will provide consent before any study data is collected.

Efforts to reduce risk are as follows:

a) Risk of using e-cigarettes: The risk of side effects and adverse events are very low. These products are sold online, and at e-cigarette specialty stores and convenience stores nationwide, without a prescription. Nevertheless, all participants will be screened for general medical precautions (pregnancy, cardiovascular disease) and monitored for adverse events during the study period. Study personnel will assess for adverse events via self-report at all follow-up visits. Any serious adverse events will be reported to the study's DSMB, then to the Ohio State University IRB, and to the NIH. We will withdraw participants who have a serious adverse event, or become pregnant, begin to breastfeed, or have a cardiovascular or pulmonary event during the study. The most likely adverse event (potential for nicotine overdose) is anticipated to be rare (<5% in our team's previous studies) and mild (nausea, headache, disrupted sleep), and will be handled quickly (i.e., advice to participant to reduce or stop EC use). Lab studies of toxin exposure suggest that ECs incur no greater risk to health than do conventional cigarettes. Indeed, e-cigarettes generally show lower levels of harmful and potentially harmful constituents. To date, e-cigarette studies discussing adverse events report mild and tolerable side effects that generally resolved completely over time with continued use; the most predominant of which were mouth/throat irritation, cough, and headache. In four randomized clinical trials, no serious adverse events were reported and the ecigarette group and the nicotine patch group had comparable levels of adverse events in two

studies. The most common were mouth irritation, throat irritation, dry cough and headache. Following the completion of the study, we will encourage all participants to quit their use of ecigarettes and they will be provided the number to the North Carolina Tobacco Quitline (QuitlineNC).

- **b)** **Risk of radiation exposure**: The risks of radiation exposure are minimized with the use of a CT scan at a very low dose and the lowest dose of [¹¹C]-nicotine (3 mCi) used in a nicotine PET imaging study. However, participants' level of risk from this level of exposure will be explained by giving them a comparison to an everyday situation to help them make an informed decision. Participants will be told, "To give you an idea about how much radiation you will get, we will make a comparison with an every-day situation. Everyone receives a small amount of unavoidable radiation each year. Some of this radiation comes from space, and some comes from naturally-occurring radioactive forms of water and minerals. This dosage would give your body the equivalent of about 5 extra months' worth of this natural radiation. A possible health problem seen with radiation exposure is an increased cancer risk. This extra cancer risk is higher at younger ages and for girls and women. The extra lifetime risk of dying of a fatal cancer due to the radiation exposure from this research may range from about one in 49,000 to about one in 20,000. At such low radiation exposures, scientists disagree about the amount of risk. These estimates are very uncertain, and there may be no extra risk at all."
- c) Loss of Confidentiality and Privacy: Study subjects' confidentiality will be maintained at all times. Subjects will be assigned a unique study identification number (study ID). All study data will be identified by study ID only. Any electronic information (e.g., questionnaire data, laboratory data, tracking systems, etc.) will only be accessible to authorized study personnel who have the necessary password(s). All computer systems will be password protected against intrusion; all network-based inter-site communications of confidential information will be encrypted. Access to computer-stored information will require simultaneous knowledge of the data format, computer language, file name and passwords. Participant information will be accessible only to research staff, who are pledged to confidentiality and complete training in the ethical conduct of research (i.e., both HIPAA and CITI trainings). Identifying information will not be reported in any publication.
- d) Lack of Appropriate Storage of EC Products: Participants will be instructed to keep their EC cartridges up and away from their children and pets to protect against unintentional poisoning. Only child-proof e-liquid cartridges will be provided to participants. Although overdose or accidental ingestion is very unlikely and has not occurred in [name] previous studies, all participants will be provided the state and national poison control telephone line as well as a "tip sheet" on recognizing signs of nicotine overdose.

iii. COVID-19 Considerations

Assuming COVID-19 is still active in the population at the start of the study, all subjects will follow best practices for clinical screening of COVID-19 prior to each visit and on the day of the visit will be in effect at Wake Forest. Participants will be screened prior to arriving on campus for COVID-19 symptoms and exposures. On campus, they will have their temperature taken and required to wear a mask. Staff will wear masks, face shields, gloves and gowns during the study procedures. If antibody testing is validated at any time during the study, this will be incorporated into the screening. Research staff will follow OSU/WF policies by wearing face masks and eye protection, using frequent hand hygiene, and gloves

when touching a participant. Disinfectant policies after each visit also will be followed. At the start of study, and at any time clinical protocols may change, these will be adopted.

iv. Potential Benefits of the Proposed Research

Whereas no assurance can be made to an individual participant that he/she will personally benefit from this research, the experience should be beneficial. In general, this study will provide a benefit to future e-cig users as the findings will be reported to public health officials and the FDA to inform policy, both for reducing toxicity (if any) and to identify harmful effects. All participants will be encouraged to quit using e-cigarettes at the completion of the study. Adequate protections are in place in the event of unlikely and mild risks for study participation. Research results will not be returned to the subject. Overall, it is expected that the potential benefits to participants in the proposed study outweigh the potential risks.

v. Importance of Knowledge to be Gained

This study is an innovative investigation that will have important public health implications given the rapid proliferation of e-cigarettes. The study has the potential for high public health impact as it will provide the scientific foundation, the FDA, and other public health agencies need to establish effective regulatory strategies for the manufacture, distribution, and marketing of nicotine salt-based ECs.

L. Data and Safety Monitoring Plan

i. Plan

Collection of Adverse Events: The collection of adverse events will be on a self-report basis by the participant and logged by research staff within an electronic data capture system (REDCap) or collected using standardized paper forms and will only be identified with the study's ID of the participant. All Serious Adverse Events will also be reported in OnCore database by Ohio State research staff.

Adverse Event Reporting Timelines:

- All intervention staff are required to notify the PIs of any Serious Adverse Events immediately.
- All Serious Adverse Events will be reported immediately to the medical monitor who will determine their severity and appropriate action or response.
- In accordance with current standard procedure, the PIs will notify the Ohio State University IRB of all Serious Adverse Events within 24 hours.
- In accordance with new policy and procedure, the PIs will notify the National Institutes of Drug Abuse of all Serious Adverse Events within 72 hours.
- All Non-serious AEs will be reviewed weekly by the medical monitor or PI, for categorization and possible action.

Data Safety Management Plan Administration

Adverse Events: All observed or volunteered adverse events regardless of suspected causal relationship to study product will be assessed by study staff and recorded on the adverse event page(s) of the Adverse Event Form or within an electronic data capture system (REDCap). For the purpose of this study, hereafter, Study Product will be used to refer to e-cigarettes. Events involving adverse Study Product reactions or illnesses with onset during the study should be recorded. Exacerbation of pre-existing illness is defined as a manifestation (sign or symptom) of the illness that indicates a significant increase in the severity of the illness as compared to the severity noted at the start of the trial. It may include worsening or increase in severity of signs or symptoms of the illness, increase in frequency of signs and symptoms of an intermittent illness, or the appearance of a new manifestation/complication. Exacerbation of a pre-existing illness should be considered when a patient/subject requires new or additional concomitant medication or non-medication therapy for the treatment of that illness during the trial. Lack of or insufficient clinical response, benefit, efficacy, therapeutic effect, or pharmacologic action should not be recorded as an adverse event. The medical monitor at Wake Forest University, will be responsible for distinguishing between exacerbation of pre-existing illness and lack of therapeutic efficacy. For all adverse events, the PIs will pursue and obtain information adequate both to determine the outcome of the adverse event and to assess whether it meets the criteria for classification as a Serious Adverse Event requiring immediate notification to the medical monitor. For all adverse events, sufficient information should be obtained by the PIs to determine the causality of the adverse event (i.e., Study Product or other illness). The PIs are required to assess causality and indicate that assessment on the Case Report Form. Follow-up of the adverse event, after the date of therapy discontinuation, is required if the adverse event or its sequelae persist. Follow-up is required until the event or its sequelae resolve or stabilize at a level acceptable to the investigator or his/her designated representative.

Serious Adverse Events: All Serious Adverse Events regardless of study product group or suspected relationship to Study Medication must be reported immediately to the medical monitor, then to IRB, then to NIDA, and in OnCore. A Serious Adverse Event is any adverse study product experience occurring at any dose that: (1) results in death; (2) is life-threatening; (3) results in inpatient hospitalization or prolongation of existing hospitalization; (4) results in a persistent or significant disability/incapacity; or (5) results in congenital anomaly/birth defect. Important medical events that may not result in death, be life-threatening, or require hospitalization may be considered Serious Adverse Events when, based upon appropriate medical judgment, they may jeopardize the patient/subject and may require medical or surgical intervention to prevent one of the outcomes listed in this definition. Any Serious Adverse Event or death must be reported immediately independent of the circumstances or suspected cause if it occurs or comes to the attention of the principal investigator at any time during the study through the last follow-up visit required by the protocol or 30 days after the last administration of Study Product, whichever comes later. Any Serious Adverse Event occurring at any other time after completion of the study must be promptly reported if a causal relationship to Study Product is suspected. The only exception to these reporting requirements is Serious Adverse Events that occur during a period in which no study product is administered. For all Serious Adverse Events, the investigator is obligated to pursue and provide information as requested by the Ohio State University IRB in addition to that on the Adverse Event Form. In general, this will include a description of the adverse event in sufficient detail to allow for a complete medical assessment of the case and independent determination of possible causality. Information on other possible causes of the event,

including concomitant medications and illnesses, must be provided. The PIs will ensure that information is reported immediately and information entered in the Adverse Event Form are accurate and consistent.

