All measures, summarized in Table 3, have been used and validated previously by our team. Questionnaire data will be collected electronically into a secure, encrypted database (REDCap) by a trained research assistant. Sociodemographic measures will assess participant age, sex, marital status, ethnicity, employment status, occupation, years of education, and socioeconomic status. Tobacco use history will assess years of tobacco use, age of first use, tobacco type, brand, frequency, quantity, and duration of use all of nicotine/tobacco products including cigars, cigarillos, little cigars, pipe tobacco, chewing tobacco, snuff, snus, EC/vape/mod/APV/e-hookah, and hookah tobacco. EC Dependence will be measured with a modified 12-item Cigarette Dependence Scale²¹. Abuse liability of products will be measured by self-report of subjective effects, including an adapted version of the Drug Effects/Liking Questionnaire will assess the desire and liking of both study products, positive and negative effects (i.e., side effects), and perceived strength and effectiveness. The modified Cigarette Evaluation Questionnaire (mCEQ)²² will also assess subjective responses to e-cigarettes (e.g., reward, satisfaction)^{23,24}. EC puff topography will be measured with the study EC device, including measures of puff count, puff duration, inter-puff-interval, puff flow rate, average puff volume, and total puff volume. Puff topography is a validated and sensitive behavioral measure of abuse liability, is highly stable and associated with level of dependence, and predicts level of exposure to harmful tobacco-related toxicants²⁵⁻²⁷. To corroborate 12-hour nicotine abstinence prior to visits 2 and 3, e-cigarette urges/craving will be measured using the 10-item Tiffany-Drobes Questionnaire of Smoking Urges: Brief Form ²⁸. A modified version (replacing the word "cigarette" with "e-cigarette") for e-cigarette users and use conditions. Additionally, nicotine withdrawal will be assessed using the empirically validated 15item version of the Minnesota Nicotine Withdrawal Scale²⁹.

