 $[^{11}C]$ -nicotine formulated with a specific eLiq (protonated or free-base) will be produced at the Wake Forest PET Research Center. Subjects will be inhaling a single puff of vapor containing $[^{11}C]$ -nicotine in either protonated or free-base e-Liquid (10 µL). Dynamic 0-15 min PET imaging will be obtained in the head-neck regions followed by a 5 min chest (oral cavity-lungs) scan. The same scan will be repeated with both the e-liquid formulations with 0-15 min chest and 5 min head scans. The subject will be scanned for 15 min in a sequence of 245 frames of 1-4 sec each. Followed by it, a 5 min scan is obtained from regions below the head i.e., oral cavity, trachea, esophagus, bronchi and lungs. All the images will be conducted using GE PET/CT Discovery MI DR scanner. Whole brain radioactivity will be calculated as a percentage of total absorbed dose

per kilogram of brain tissue. Standard uptake values (SUVs), Time activity curves (TACs), and percent variance in total radioactivity will be determined and compared at each time point.

Table 3: Study Measures and Outcomes				
Visit	1	2	3	
Background Measures				
Additional Screening	Х			
Sociodemographic Measures	Х			
Tobacco Use History/Dependence	Х			
NicAlert Test Strip	Х			
Medical History	Х			
Abuse Liability				
EC Topography		Х	Х	
Drug Effects/Liking Questionnaire		Х		
Modified Cigarette Evaluation Questionnaire (mCEQ)		Х		
Tiffany-Drobes Questionnaire of Smoking Urges: Brief Form (modified)		Х	Х	
Minnesota Nicotine Withdrawal Scale		Х	Х	
Biomarkers of Exposure/Effect				
Exhaled Carbon Monoxide	Х	Х	Х	
Procedures				
Pregnancy Test	Х	Х	Х	
PET/CT Imaging		Х	Х	

I. Statistical Methods

i. Power Analysis and Data Analytic Plan

The present study is a pilot study that will be used for preliminary data for a larger R01 submission. Assuming an alpha value of 0.05 and a power of 0.8, a sample size of at least 8 participants is required to observe significant differences in the dose released. As a result, larger populations are likely required in order to evaluate a significant difference between the groups. If the power is set to 0.95 to account for this, then the number of participants required per group is 14. In order to ensure significance and to account for any participants that do not comply, a total of 30 participants is required.

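### Craving and withdrawal are compared between nicotine forms as post-minus-pre change; adjusting for the score before the visit's first puff would usually be more precise, by an amount that depends on a correlation the plan does not give

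*Combined protocol and SAP*

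**What the plan says.** Section I.i (Power Analysis and Data Analytic Plan) will "compare the difference in mean outcomes (post – pre-vaping bout, where appropriate) per laboratory session", using a random-effects model that it describes as conceptually a paired t-test or a signed-rank test. It names no baseline covariate. Its list of compared outcomes includes craving and withdrawal suppression, and it treats each participant as their own control.

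Section H (Measures) says "e-cigarette urges/craving will be measured using the 10-item Tiffany-Drobes Questionnaire of Smoking Urges: Brief Form", with corroboration of the 12-hour abstinence as the stated purpose. A withdrawal scale is assessed for the same purpose. Table 3 marks both scales at Visits 2 and 3, the two visits at which the forms are compared, but gives no time within the visit. Under Visit #2 in Section E.ii, each visit has two single-puff bouts with the same e-liquid.

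The sample size was set "to observe significant differences in the dose released". Nothing is powered on craving or withdrawal.

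**The concern.** In a parallel-group trial, subtracting a baseline removes between-person variation. Here the crossover has already removed it. What the visit-specific pre-score can still explain is the visit-to-visit part, such as how strongly the person craves on that day. Subtraction fixes the coefficient for that part at 1, whatever the data say, and carries the measurement error of the pre-score into the contrast. A fitted coefficient takes out only the part that predicts the post-score.

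At stake is the precision of the craving and withdrawal contrasts in a study that may finish with about 24 people. Day-to-day abstinence may well vary: the exhaled-CO check at Visit 2 is described as confirming abstinence from combustible products, and Table 3 lists the NicAlert strip at Visit 1 only. The urges and withdrawal scores are then the scheduled information on vaping abstinence at the two form visits, and the analysis uses them only by subtraction.

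**Working it through.** **The plan's own figures.** The text reads "Assuming an alpha value of 0.05 and a power of 0.8, a sample size of at least 8 participants is required", then "the number of participants required per group is 14" at power 0.95, then "a total of 30 participants is required". No effect size or SD is given, so these cannot be derived, only checked against each other. Since "All statistical tests will be two-tailed", scaling from 80% to 95% power multiplies n by [(1.960 + 1.645)/(1.960 + 0.842)]² = 1.656, and 8 × 1.656 = 13.2, which rounds up to 14. The two figures fit each other. They concern dose released, so they do not bear on the choice examined here.

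**Inputs.**
- Completers: 30 enrolled with 20% attrition (Section F.i) gives 30 × 0.8 = 24.
- r: the correlation, across participants, between the between-visit difference in the pre-score and that in the post-score. Not in the documents; assumed range 0 to 0.95.
- Equal variances of those two differences: assumed, and relaxed below.

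**Formulas.** With unit variances, the form contrast has variance proportional to:
- change score: 2(1 − r)
- baseline-adjusted: 1 − r²
- adjusted/change in large samples: (1 − r²)/[2(1 − r)] = (1 + r)/2
- cost of estimating the slope, with period in the model: 1 + 1/(n − 4) = 1 + 1/20 = 1.05 at n = 24

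| r | Change | Adjusted | Large-sample ratio | Ratio at n = 24 | CI-width ratio | Adjusted power if change score has 80% |
|---|---|---|---|---|---|---|
| 0 | 2.00 | 1.00 | 0.50 | 0.53 | 0.73 | 97% |
| 0.3 | 1.40 | 0.91 | 0.65 | 0.68 | 0.83 | 92% |
| 0.5 | 1.00 | 0.75 | 0.75 | 0.79 | 0.89 | 88% |
| 0.7 | 0.60 | 0.51 | 0.85 | 0.89 | 0.95 | 84% |
| 0.9 | 0.20 | 0.19 | 0.95 | 1.00 | 1.00 | 80% |

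The post-score alone has variance 1 on this scale. Below r = 0.5 the change score is therefore noisier than ignoring the baseline altogether.

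A simulation with 2,000 runs per setting at n = 24, using the between-visit baseline difference as covariate, gave ratios of 0.52–0.54, 0.67–0.69, 0.78–0.81, 0.90 and 1.01–1.02 for the five rows.

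**Where the gain ends.** Break-even is at (1 + r)/2 × 1.05 = 1, so r = 2/1.05 − 1 = 0.90. The same sum gives 0.82 at n = 14 and 0.93 at n = 30. The worst loss computed was at n = 14 and r = 0.95: 0.975 × 1.10 = 1.07, or 7% more variance. At n = 24 and the same r it is 0.975 × 1.05 = 1.02.

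**Unequal variances.** With k the pre/post SD ratio, the large-sample ratio is (1 − r²)/(1 + k² − 2kr). At k = 0.5 and r = 0.5 it is 0.75/0.75 = 1.00. There the true within-person slope r/k is 1, so subtraction is already the best use of the baseline.

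**Topography with pre-puff urges as covariate.** No baseline is used for topography now, so the comparison is with the unadjusted contrast: (1 − r²) × 1.05, with r here the correlation of the between-visit differences in urges and in the topography measure. This gives 0.91 × 1.05 = 0.96 at r = 0.3, 0.84 × 1.05 = 0.88 at 0.4 and 0.75 × 1.05 = 0.79 at 0.5. Break-even is at r = √(1 − 1/1.05) = 0.22.

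**The case against.** A change score in a randomised crossover is unbiased. This is a pilot, its sample size rests on another outcome, and r is unknown. After a single puff the same-scale pre and post scores could be so highly correlated that little is gained. All of that stands. It makes this a point about precision, not validity, and the PET outcomes of Aim 2 are untouched.

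Timing is also less settled than the analysis text suggests. That the scales precede the puff is inferred from their abstinence purpose. A post-bout administration is implied by the analysis wording and by withdrawal suppression as an outcome, but Section E.ii schedules neither. This stands too, and the fix has to supply the timing.

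A reader might go further in three ways that the documents do not support:
- **That adjustment is sure to give a tighter contrast.** The large-sample advantage is not a guarantee at 24 people. Leaving out the small-sample cost would put the change-score variance 54%, 33% and 18% above the adjusted one at r = 0.3, 0.5 and 0.7; with it the figures are 47%, 27% and 12% (1/0.6825, 1/0.7875, 1/0.8925).
- **That liking and mCEQ satisfaction would gain as well.** Table 3 marks both questionnaires at Visit 2 only, so as scheduled each person rates one form and there is no within-person contrast to adjust. Section E.ii describes Visit #3 as nearly the same as Visit #2, so the table may be at fault; the two places must be reconciled first.
- **That craving on the day evidently drives puffing.** The documents give no correlation between urges and puff duration, volume or flow.

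**Conclusion.** The point holds for craving and withdrawal. Using the pre-bout score only by subtraction is usually the less precise choice in this crossover. If r lies between 0.3 and 0.7, adjustment is expected to remove about 32% to 11% of the contrast's variance at 24 completers. The result rests on an assumed r, roughly equal pre and post variances, and scales given both before the first puff and after the bout at both form visits. The gain vanishes near r = 0.9 or with a true slope of 1, and the possible loss is a few percent. For topography, adjustment is exploratory only. For liking and the mCEQ no conclusion can be drawn until the visit schedule is settled.

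**What to change.** In Section I.i, for craving and withdrawal, replace the change score by a model of the post-bout value with the same scale's score from before the first puff of that visit as covariate. Enter it as the within-person difference between the two visits, so that the slope is a within-person one. Report the change-score contrast alongside.

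In Section E.ii and Table 3, state that this baseline score is completed before the first puff at Visits 2 and 3, and state when the post-bout score is taken. A score taken before the second bout follows exposure to the same form and must not serve as the baseline.

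If topography is to be adjusted for pre-puff urges, label that exploratory. Reconcile Table 3 with the Visit #3 description before specifying any form contrast for liking or the mCEQ.

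The cost is about one degree of freedom, a few percent of variance if r is very high, and a short note on questionnaire timing. No added visits, scans or participants are needed, and the stated sample size is unaffected.

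### The exception for serious adverse events in product-free time contradicts the reporting duties stated just before it; separately, two sections name different first recipients

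*Combined protocol and SAP*

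**What the plan says.** All references are to the combined protocol and SAP.

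**Section L, Serious Adverse Events.** Three consecutive sentences set the scope of reporting.

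- An SAE or death must be reported immediately, whatever its cause, "if it occurs or comes to the attention of the principal investigator at any time during the study" and "through the last follow-up visit required by the protocol or 30 days after the last administration of Study Product, whichever comes later".
- Any SAE "occurring at any other time after completion of the study must be promptly reported if a causal relationship to Study Product is suspected".
- Then: "The only exception to these reporting requirements is Serious Adverse Events that occur during a period in which no study product is administered".

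**Section L.i, Adverse Event Reporting Timelines.** "All Serious Adverse Events will be reported immediately to the medical monitor", and the PIs notify the IRB within 24 hours and NIDA within 72 hours. No exception is given.

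**Section L, Adverse Events.** All observed or volunteered adverse events are recorded regardless of cause, and the PIs judge whether each is serious. For the study's purposes, "hereafter, Study Product will be used to refer to e-cigarettes".

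**Section K.ii, risk of using e-cigarettes.** "Any serious adverse events will be reported to the study's DSMB", then to the IRB and the NIH. The medical monitor is not in this chain.

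**The concern.** The time after the last administration is, by the meaning of the words, time in which no product is administered. An exception for such time therefore works against a window that is counted from the last administration. It also works against the duty to report later events suspected to be related.

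Two members of staff who follow the same paragraph could reach opposite decisions about a hospitalization or death in the weeks after Visit 3. The same applies between the two PET visits. An SAE in that gap is one the medical monitor is meant to assess before further dosing, and Section K.ii says that participants who have an SAE are withdrawn.

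The routing discrepancy is a smaller matter: a reader of Section K.ii and a reader of Section L would notify different people first.

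**Working it through.** No statistical figure is involved, so the check is one of text against text.

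**Step 1: which limb of the window applies.** Table 1 ends with Visit 3b and debriefing and shows no later visit. If the last study puff is taken at Visit 3b on day D, the last visit is also day D. The later of D and D + 30 is D + 30, so the 30-day limb governs. This assumes no study-product use after Visit 3.

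**Step 2: how much of that limb the exception covers.** Days after the last administration on which product is administered: 0 of 30. Days on which an SAE with onset would be exempt on a literal reading: 30 − 0 = 30. This follows from the word *after* alone and says nothing about how many events would be missed.

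**Step 3: the rules applied to each kind of event.**

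| Onset of the SAE | Window and post-study sentences | Timelines list | Exception, read literally |
|---|---|---|---|
| During the study, before the first product use at Visit 1 | Report | Report | Exempt |
| During product use (Visit 1 sampling, take-home practice, PET puffs) | Report | Report | Not exempt |
| During product use, but learned of later within the window | Report | Report | Not exempt |
| Product-free time between Visits 2 and 3 | Report | Report | Exempt |
| Days 1 to 30 after last use | Report | Report | Exempt |
| After day 30, relation suspected | Report | Report (no time limit stated) | Exempt |

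The rules disagree in four of the six rows. In the first row an exemption would do little harm. The other three are the rows where the preceding sentences and the exception cannot both be followed.

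**Step 4: is the gap between Visits 2 and 3 product-free?** Section E.ii (Visit #2) asks for at least 1 week between these visits. Section F.iii pays participants an extra $20 to bring the device back at Visit 2. This suggests little or no home use of the study product afterwards, but the protocol does not say so.

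**Step 5: is the exempt period defined?** It is not. The text gives no length of time after a puff at which a product-free period begins. Study Product is defined only as e-cigarettes, and the participants are current users with at least one vaping bout per day. If their own devices counted, product-free time would be short. If only the study device counts, which the word *administered* suggests, it would be most of the calendar.

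**Step 6: routing.** Section K.ii: DSMB, IRB, NIH. Section L: medical monitor, IRB, NIDA, with entry in OnCore. NIH and NIDA need not conflict. The first recipient does differ. A DSMB is mentioned once in Section K and not at all in Section L.

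**The case against.** The best defence is that the exception was meant narrowly, for example for screening time before any exposure. On that reading the two sentences before it keep their full effect, and the unqualified timelines list supports it. The intent is plausible, but the text does not state it, and staff have to work from the text.

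Several stronger readings are tempting and do not hold.

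- *That the 30-day window is void.* It is not. The window also covers SAEs that come to the PI's attention within it, so an event with onset during product use and discovered later stays reportable.
- *That events would go unrecorded, or that the SAE count is shown to change.* The exception concerns reporting. The Adverse Events paragraph still requires recording, a judgement of seriousness, and follow-up of events that persist. Section K.ii has staff ask about adverse events at follow-up visits. Capture is less clear after the last visit, but a changed count is not established.
- *That 30 of 30 days measures lost safety information.* The figure is true by definition and estimates no risk.
- *That the radiolabelled aerosol makes delayed events a particular worry.* The radiation harm described in Section K.ii is lifetime cancer risk, which no 30-day window would capture.
- *That the study has no DSMB.* Section K.ii speaks of one as existing, and a passage of the document was not available for review. The documents show only that Section L gives it no role. Both routes reach the IRB and NIH or NIDA, so following Section K.ii does not leave an SAE unreported.

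What stands after these objections is the contradiction in the three rows of Step 3 and the difference in first recipient.

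**Conclusion.** The exception is wrong as written. It contradicts the two sentences before it and the duty in the timelines list to report all SAEs. Read literally, it exempts every SAE with onset after last product use, including later events suspected to be related, as well as SAEs in product-free time between Visits 2 and 3. The last part assumes that the study product is not used at home after Visit 2, which the device-return payment suggests but does not prove.

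This is an internal contradiction in safety reporting. It does not touch the sample size, the outcomes or the analysis. Its effect on the number of reported events cannot be estimated from the documents. It still merits correction before the plan is used, because it bears on whether deaths and hospitalizations are reported and is easily repaired. The routing discrepancy is real but secondary.

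**What to change.** 1. Delete the exception sentence, or limit it to events before first study-product exposure, which occurs with the e-liquid sampling at Visit 1. If it is kept, define the period with reference to the study device and e-liquids, since the present definition of Study Product does not do so.
2. Do not extend the exception to events after the 30-day window. That would look tidy, but it would cancel the duty to report later SAEs suspected to be related.
3. Make Sections K.ii and L state one reporting route. Either name the medical monitor as first recipient in Section K.ii, or describe the DSMB's role in Section L.

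The cost is about two sentences of protocol wording, and possibly a few more SAE reports in a study of up to 30 participants. No visit, measurement or analysis changes.
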